#### AMENDMENT HISTORY

Version Number	Revision Date (DD/MM/YYYY)	Reasons for Revision
1.0	18 November 2018	Original Draft

#### ABBREVIATIONS

AE	adverse event
CI	confidence interval
CRF	case report form
CSR	Clinical Study Report
DMC	Data Monitoring Committee
eCRF	electronic case report form
FDA	Food and Drug Administration
ICH	International Conference on Harmonization
ITT	Intent-to-Treat
IVRS	interactive voice response system
LOCF	last observation carried forward
PI	principal investigator
SAE	serious adverse event
SAP	Statistical Analysis Plan
SD	standard deviation

## 1. INTRODUCTION

This statistical analysis plan (SAP) describes the analyses and data presentations for protocol CR-6305 Version 4.0 Amendment 3.0.

This document will serve as the final guidance for all the statistical analysis for this study and will supersede the Statistical Method section in the protocol if there are any discrepancies. Any deviation from the analysis plan will be documented as such in the clinical study report.

## 1.1. Study Objectives

Primary Objectives:

The primary purpose of this randomized study is to demonstrate that the 4GT Test lens senofilcon A with new UV-blocker, in its final lens design ECL600, meets the design validation requirements related to overall CLUE comfort, logMAR visual acuity, quality of vision in bright light, eye health, and fit acceptance.

#### Secondary Objective:

The secondary objective of this study is to demonstrate that the Test lens is equal or better than marketed product senofilcon A (ACUVUE® OASYS, Johnson & Johnson Vision Care, Inc.) with regards to overall CLUE vision and handling.

Other observations of interest include adverse events, keratometry, surface characteristics (deposits and wettability), daily wear time, reasons for discontinuation, and lens damage.

## 2. STUDY DESIGN

### 2.1. Overview

This study is a randomized, 2-visit, partially subject-masked, 2-arm parallel, dispensing trial. Approximately 236 subjects (118 subjects /arm) will be screened and enrolled to ensure that at least 224 subjects (112 subjects/arm) complete the study.

The study begins with an initial visit (Visit 1). If a subject is found to meet all eligibility criteria, they will be randomized to one of two study lenses (Test or Control) in a bilateral fashion.

If the subject is dispensed study lenses at the initial visit, one follow-up visit will be conducted. The follow-up visit will occur approximately two weeks after the initial visit. Unscheduled follow-up visits may occur during the study. Subjects will be advised to wear the study lenses at least five (5) days per week for at least six (6) hours per day for a period of two weeks. There is no planned lens replacement scheduled during this study.

#### 2.2. **Test Articles**

Table 1: Test Article Labels

Test Article	Label	Report Labels
senofilcon A based contact lens with new UV-	Test	Acuvue ® Oasys with
blocker		Transitions ™
ACUVUE® OASYS Brand Contact Lenses with	Control	Acuvue® Oasys
HYDRACLEAR ® PLUS		
All Test Articles	Total	Total

#### 2.3. **Targeted Study Population and Sample Size**

Approximately 236 subjects will be enrolled to ensure that at least 224 subjects will complete the study (~112 per/arm). Enrolled subjects will be habitual wearers of spherical contact lenses. All subjects will be the age of 18 and  $\leq$ 49 years old. Eligible presbyopes will be those that wear full distance contact lenses in both eyes, then wear reading glasses over them. Subjects will wear the Test or Control contact lenses approximately 2 weeks each in a bilateral fashion as DW.

	Test	Control	Total
Enrolled	118	118	236
Randomized	116	116	232
Completed	112	112	224
Number of enrolled per site	10-12	10-12	20-24

Table 2: Planned Enrollment Strategy by Lens type and Site

#### 2.4. Test Article Allocation and Masking

Using a computer-generated randomization scheme will be used to randomly assign subjects, in blocks of 2, to one of the two possible study lenses (TEST or CONTROL). The random scheme will be generated using the PROC PLAN procedure from SAS Software Version 9.4 or higher (SAS Institute, Cary, NC).

The study site must follow the randomization scheme provided and complete enrollment according to the randomization list and not pre-select or assign subjects. The randomized assignment of subjects will be performed at the first visit prior to the first fitting. The following must have occurred prior to randomization:

- Informed consent has been obtained
- Subject meets all the inclusion / not meets exclusion criteria
- Subject history and baseline information has been collected.

The dynamic nature of the Test lens makes it impossible to completely mask the study lens assignment. The subjects will be aware if they are wearing a photochromic lens or nonphotochromic lens due to the function nature of the photochromic dye. Additionally, there is a slight difference in physical appearance between the Test and Control lenses when the Test lens CR-6305, Statistical Analysis Plan Version 1.0

is activated by outdoor light that makes it difficult to mask investigative personnel. However, the control lens will be masked in the event that OASYS is the subject's habitual lens by chance, making this a partial-subject masked study.

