4. STUDY DESIGN AND RATIONALE

4.1. Description of Study Design

This study is a randomized, 2-visit, partially subject-masked, 2-arm parallel, dispensing trial. Approximately 236 subjects (118 subjects /arm) will be screened and enrolled to ensure that at least 224 subjects (112 subjects/arm) to complete.

The study begins with an initial visit (Visit 1). If a subject is found to meet all eligibility criteria, they will be randomized to one of two study lenses (Test or Control) in a bilateral fashion.

If the subject is dispensed study lenses at the initial visit, one follow-up visit will be conducted. The follow-up visit will occur approximately two weeks after the initial visit. Unscheduled followup visits may occur during the study. Subjects will be advised to wear the study lenses at least five (5) days per week for at least six (6) hours per day for a period of two weeks. There is no planned lens replacement scheduled for during this study.

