4.3. Enrollment Target and Study Duration

- Approximately 112 subjects are targeted to complete the Test arm of the study, and an additional 112 subjects are targeted to complete the Control arm of the study.
- 10 clinical sites will be recruited to participate, and each site will enroll approximately 20-24 subjects.
- Enrollment is defined at the point when the Informed Consent is signed. Termination is defined at the completion of the Final Evaluation.
- Each site will have approximately 2 weeks to enroll all their subjects unless otherwise approved by the Sponsor. Each subject will be in the study approximately 2 weeks, making the entire study approximately 4 weeks in duration.

	Test	Control	Total
Randomization	116	116	232
Completion	112	112	224
Number of sites	10	10	10
Subjects/site (Min-Max)	10-12	10-12	20-24

Table 2: Target number of subjects by arm and site

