5. TEST ARTICLE ALLOCATION AND MASKING

5.1. Test Article Allocation

A computer-generated randomization scheme will be used to randomly assign subjects, in blocks of 4, to one of the two possible study lenses (TEST or CONTROL). The random scheme will be generated using the PROC PLAN procedure from Statistical Analysis System (SAS) Software Version 9.4 or higher (SAS Institute, Cary, NC).

The study site must follow the randomization scheme provided and complete enrollment according to the randomization list and not pre-select or assign subjects. The randomized assignment of subjects will be performed at the first visit prior to the first fitting. The following must have occurred prior to randomization:

- Informed consent has been obtained
- Subject meets all the inclusion / not meets exclusion criteria
- Subject history and baseline information has been collected.

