5.2. Masking

The dynamic nature of the Test lens makes it impossible to completely mask the study lens assignment. The subjects will be aware if they are wearing a photochromic lens or non-photochromic lens due to the function nature of the photochromic dye. Additionally, there is a slight difference in physical appearance between the Test and Control lenses when the Test lens is activated by outdoor light that makes it difficult to mask investigative personnel. However, the Control lens will be masked in the event that OASYS is the subject's habitual lens by chance, making this a partial-subject masked study.

Every attempt will be made to keep the other clinical trial personnel involved in the study (e.g. Data management, Biostatistician and Clinical Operations) unaware of the lens assignment. The identity of the study lenses will be masked by over labeling the blister packs with a label containing the study number, lot number, sphere power, expiration date and the randomization codes. Only the personnel involved in the over labeling and the Statistician generating the randomization scheme will have access to the decode information translating the randomization codes into Test and Control arms. The medical monitor will also have access to the decode information in case breaking the mask is necessary for the urgent medical treatment of a subject.

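### The protocol randomises in blocks of 4 and the SAP in blocks of 2; nothing reconciles them, and the smaller block would make up to half of the assignments deducible

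*SAP*

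**What the plan says.** Protocol 5.1 (Test Article Allocation) has a computer-generated scheme assign subjects "in blocks of 4, to one of the two possible study lenses". SAP 2.4 (Test Article Allocation and Masking) repeats that paragraph almost unchanged but has "in blocks of 2, to one of the two possible study lenses". Neither document explains the difference.

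SAP 1 (Introduction) says that the SAP "will supersede the Statistical Method section in the protocol if there are any discrepancies". Allocation is in Protocol Section 5; the statistical methods are in Section 14.

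On masking, Protocol 5.2 and SAP 2.4 say that subjects will know whether their lens is photochromic. They add that a slight visible difference, when the Test lens has been activated by outdoor light, "makes it difficult to mask investigative personnel". Protocol 6.4 gives the two lenses different packaging: over-labelled commercial blisters for Control, and blisters with an investigational foil for Test. Under Protocol 5.3, site staff consult the scheme themselves, enter the subject's number on the appropriate line and take the lenses from stock. Neither document describes central concealed allocation, varying block sizes, or whether blocks run within site.

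**The concern.** Two block sizes for one list cannot both be right, and a reader cannot tell from the documents which list was generated.

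In a fully masked trial this would be close to a clerical matter. Here the lens can be recognised, and with a small fixed block a recognised assignment carries information about the next one. Site judgement operates before randomisation: the investigator judges whether a subject appears able and willing to comply, judges whether an ocular abnormality would interfere, and may repeat the baseline slit-lamp check once (Protocol 3.2, 3.3 and 7.2). Someone who could deduce the next lens could, deliberately or not, influence who is enrolled and when.

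The endpoints most exposed are comfort and satisfaction with vision in bright light. Both are primary and patient-reported, and every primary hypothesis must be met (Protocol 2.3.1, SAP 4.1). The comfort model adjusts for baseline comfort. The bright-light model has no baseline rating: SAP 10.1 names lens as the only fixed effect, with other characteristics when appropriate, and the code in SAP 14.1 adds only age and sex, with site as a random effect. Selective enrolment related to that item would therefore not be corrected by a baseline score.

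**Working it through.** A block size is a design choice, so there is no stated power or alpha to reproduce. Three checks apply.

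**1. Does a precedence rule settle the conflict?** The SAP's clause names the protocol's statistical section. The block size is in Protocol 5.1, outside that section. The clause does not clearly make either size govern.

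**2. Do the planned numbers reveal the size?** Allocation is 1:1 ("Approximately 236 subjects (118 subjects /arm) will be screened and enrolled"), with 232 to be randomised (Protocol Table 2, SAP Table 2), and "each site will enroll approximately 20-24 subjects".

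- 232 / 4 = 58 and 232 / 2 = 116
- 236 / 4 = 59 and 236 / 2 = 118
- 20 / 4 = 5 and 20 / 2 = 10; 24 / 4 = 6 and 24 / 2 = 12

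All are whole numbers. A site of 22 would leave a block of 4 incomplete (22 / 4 = 5.5), but site numbers are approximate, so this excludes nothing.

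**3. How predictable is each size?** Take all balanced orders within a block as equally likely. An assignment is deducible if the earlier ones in its block leave only one arm. The best guess is the arm with more places left, or a coin toss when the places are equal.

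*Blocks of 2* (orders TC, CT):
- The second place always follows from the first: 1 of 2 = 50%; 232 × 0.5 = 116, or 10 to 12 at a site of 20 to 24.
- Correct guesses: (1/2 + 1) / 2 = 3/4 = 75.0%.

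*Blocks of 4* (orders TTCC, TCTC, TCCT, CTTC, CTCT, CCTT):
- The fourth place is always deducible. The third is deducible only in TTCC and CCTT, that is 2 of 6.
- Share: (1 + 1/3) / 4 = 1/3 = 33.3%; 232 / 3 = 77.3, or 6.7 to 8 per site.
- Correct guesses by place: 1/2; 2/3; (1/3 × 1) + (2/3 × 1/2) = 2/3; 1. Their sum is 17/6, and 17/6 / 4 = 17/24 = 70.8%.

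| Fixed block size | Deducible | Of 232 | Best guess right |
|---|---|---|---|
| 2 (SAP) | 50.0% | 116 | 75.0% |
| 4 (protocol) | 33.3% | about 77 | 70.8% |
| 6 (for comparison) | 25.0% | 58 | 68.3% |

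The same enumeration over the 20 balanced orders gives the row for 6. Moving from 4 to 2 adds about 39 deducible assignments (116 − 77.3 = 38.7) and 75.0 − 70.8 = 4.2 percentage points of guessing accuracy.

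**The case against.** The strongest reply is that this is a wording slip with no demonstrated effect. The SAP may simply misdescribe a list made in blocks of 4. Both documents require consent, eligibility and baseline data before randomisation and forbid sites to pre-select subjects. Packs carry coded over-labels. The visible difference is called slight and depends on outdoor light. Subjects learn their lens by wearing it but return on Day 13 to 15, when a site's enrolment period of about two weeks is nearly over.

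Much of this stands. A reader might infer that under the SAP every second lens is known before it is assigned. The documents do not support that: it needs within-site blocks, staff who know or infer the size, and timely recognition of the earlier lens, and none of these is stated. A reader might also infer that predictability distorts fit acceptance and dispensing. In Protocol 7.2 those steps come after the lens has been assigned; any influence there comes from incomplete masking of the current lens, which no block size changes.

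What does not stand is that the conflict is harmless. A rule against pre-selection is an instruction and does not make the next assignment unpredictable. Recognition need not wait for the subject's return, because the packaging differs and site staff handle the scheme and the packs. A slip in the SAP would still need correcting.

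**Conclusion.** The inconsistency is certain: two block sizes are stated for one list, and neither the precedence clause nor the planned totals settles which is right. A reader might take the SAP's claim to override as making blocks of 2 govern; the clause does not extend to Protocol Section 5.

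The consequence is conditional. On the three assumptions above, blocks of 2 make 50% of assignments deducible against 33.3% for blocks of 4, with best-guess accuracy of 75.0% against 70.8%. These figures measure the opportunity for selection, not bias that has occurred; the documents allow no estimate of its size or direction. The route is who is enrolled and when, and from there the comfort and bright-light comparisons. Power, alpha and sample size are unaffected.

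Nor do blocks of 4 remove the weakness, since a third of assignments would still be deducible. That is a separate reason to prefer mixed sizes and not part of the contradiction.

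**What to change.** Check the generated list first; the correction depends on what it shows.

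- **List in blocks of 4:** correct SAP 2.4 to match Protocol 5.1.
- **List in blocks of 2, already used:** keep it, correct Protocol 5.1, disclose the block size in the study report and compare baseline characteristics by arm. That comparison can show an imbalance but cannot prove there was no selection.
- **No list yet:** do not use fixed blocks of 2. Use site-specific lists with randomly mixed block sizes (for example 4 and 6). Both documents should say that sizes vary and are withheld from sites, with the sizes themselves kept in a restricted record.

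In every case, say whether blocks run within site and whether sites are told the size. Also say how much of the scheme staff can see under Protocol 5.3: if upcoming codes are visible and a code is recognised, mixing block sizes would not help.

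The cost is about one sentence per document and, for a new list, a different PROC PLAN call. Mixed sizes allow slightly larger arm imbalance within a site. Because packs are over-labelled with randomisation codes, a new list made after labelling could mean relabelling, so the choice is best settled before then.

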#### 2.5. Time and Event Schedule

 Table 3: Time and Events Schedule

Visit Information	Visit 1 Screening Baseline	Visit 2 Follow-up
	Treatment 1	Final Evaluation
Time Point	Day 1	Day $14 \pm 1$
Estimated Visit Duration	2.5 hours	1.5 hours
Statement of Informed Consent	X	
Demographics	X	
Medical History/Concomitant Medications	Х	Х
Habitual Contact Lens Information	Х	
Inclusion/Exclusion Criteria	Х	
Baseline Questionnaires	Х	
Entrance Visual Acuity	Х	
Iris Color	Х	
Keratometry	Х	Х
Subjective Sphero-Cylindrical Refraction	Х	Х
Slit Lamp Biomicroscopy	Х	Х
Lens Selection	Х	
Lens Insertion & Settling	Х	
Visual Acuity and Over Refraction	Х	Х
Lens Power Modification	Х	
Subject Reported Ocular Symptoms	Х	Х
Visual acuity (distance Snellen)	Х	Х
Lens Fit Assessment	Х	Х
Lens Wettability	Х	Х
Dispense Patient Instruction Guide	Х	
Dispense Test Article	Х	Х
Lens wear Compliance		Х
Wearing Time and Compliance		Х
Follow-up Questionnaire		Х
Distance ETDRS logMAR Visual Acuity		Х
Surface Deposits		Х
Study Completion		Х
Lens Removal and Storage		Х
Final Evaluation		х

#### 3. STUDY ENDPOINTS

#### 3.1. Primary Endpoints

Primary Efficacy Endpoints:

#### CLUE Overall Comfort

Overall comfort scores will be assessed using the Contact Lens User Experience (CLUETM) questionnaire at the two-week follow-up. CLUE is a validated patient-reported outcomes questionnaire to assess patient-experience attributes of soft, disposable contact lenses (comfort, vision, handling, and packaging) in a contact-lens wearing population in the US, ages 18-65. Derived CLUETM scores using Item Response Theory (IRT) follow a normal distribution with a population average score of 60 (SD 20), where higher scores indicate a more favorable/positive response with a range of 0-120. A 5-point increase in an average CLUETM score translates into 10% shift in the distribution of scores for population of soft contact lens wearers. The comfort scores will be generated using the flexMIRT software Version 3 or higher (Chapel Hill, NC).

#### Distance Monocular Contact Lens Visual Acuity

Distance monocular contact lens visual performance (logMAR) is assessed for each subject eye at the two-week follow-up evaluation using EDTRS charts at a 4-meter distance under the lighting condition, Bright illumination high contrast.

The subject is asked to read the visual acuity chart and the investigator will report in eCRF the letters missed by the subject and the logMAR score will be derived in eCRF. In case the subject is unable to read at least 3 letters on the top line of the chart, the investigator will repeat the assessment at a closer distance: The subject starts at 4 meters, then will be moved to 3 meters then 0.5m closer at a time (e.g. 4m, 3m, 2.5m, 2.0m). If the subject correctly reads all 5 letters on the last line, the test will be stopped, and 0 missing will be recorded without moving subjects further away from the chart.

The formula to compute logMAR score at a different distance other than the chart specified distance (i.e. 4 meters) is:

 $LogMAR_2 = LogMAR_1 + log10(D_1/D_2)$ 

where:

- LogMAR1 is the logMAR score at the chart specified distance D1;
- LogMAR2 is the adjusted logMAR score at a different distance D2.

The procedure is explained in the in Appendix D of the study protocol.

#### Vision Satisfaction in Bright Lighting

Vision satisfaction in bright lighting will be assessed using the individual item (Item ID: V015\_1) "I was satisfied with the quality of my vision in bright lighting" from the CLUETM

questionnaire. This item uses the response scale, 1: Strongly Disagree, 2: Disagree, 3: Neither Agree nor Disagree, 4: Agree and 5: Strongly Agree.

Primary Safety Endpoints:

## Slit Lamp Findings (Grade 3 or Higher)

Slit Lamp Findings will be assessed for each subject eye at all study visits (schedule and unscheduled). SLF is a binary response where Y=1 for at least one Grade 3 or 4 slit lamp finding. The percentage of eyes with Grade 3 or higher slit lamp findings will be analyzed and will include corneal infiltrates. Eyes with multiple events will be counted only once.

The FDA Biomicroscopy Scale measures the severity of the ocular clinical findings and goes from Grade 0 (none) to Grade 4 (severe). The procedure is explained in the section 12 Appendix D of the study protocol. The individual ocular finding results are considered as other endpoints.

## Fit Acceptance Rate

Acceptable lens fit will be assessed at all study visits (scheduled and unscheduled) for each subject eye. Fit acceptance rate will be based on the lens fit acceptance of eyes wearing the Test lens only. Fit acceptance is a binary response where Y=1 if lens fit is acceptable and Y=0 otherwise. Unacceptable is defined as unacceptable if any one of the following criteria:

- limbal exposure at primary gaze or with extreme eye movement;
- edge lift;
- excessive movement in primary up gaze;
- insufficient movement in all three of the following conditions: primary gaze, up gaze, and push up test.

Eyes with multiple unacceptable fitting events will be counted only once. Fit rates of the Control lens will also be collected but are not a primary endpoint.

The procedure is explained in the **section** in section 12 Appendix D of the study protocol. The individual lens fitting characteristics are considered as other endpoints.

# 3.2. Secondary Endpoints

CLUE Overall Quality of Vision and Handling

Overall Quality of vision and handling scores will be assessed using the Contact Lens User Experience (CLUE) questionnaire at the two-week follow-up.

# 3.3. Other Endpoints

- Average daily wear time (in Hours)
- Subject's Reported Ocular Symptoms
- Lens fitting characteristics

- Adverse events
- Discontinuation
- Reasons for discontinuation
- Unscheduled lens replacement
- Reasons for unscheduled lens replacement including lens damage.

## 4. STATISTICAL HYPOTHESES FOR STUDY OBJECTIVES

#### 4.1. Primary Hypotheses

All the primary hypotheses must be met in order to satisfy the primary objective of this study.

- 1. Subjects wearing the JJVCI Investigational contact lenses on a daily wear basis will have patient reported comfort at the 2-Week Follow Up visit that is non-inferior to that of subjects wearing predicate device on a daily wear basis. A non-inferiority margin of -5 CLUE points will be used.
- 2. Subjects wearing the JJVC Investigational contact lenses on a daily wear basis will report distance monocular visual acuity (logMAR: bright room luminance / high contrast charts) at the 2-Week Follow Up visit that is non-inferior to that of subjects wearing predicate device on a daily wear basis. A non-inferiority margin of 0.05 LogMAR will be used.
- 3. Subjects wearing the JJVCI Investigational contact lenses on a daily wear basis will have patient reported outcome (Agree and Strongly Agree) on the Quality of Vision in Bright Light at the 2-Week Follow Up visit that is non-inferior to that of subjects wearing predicate device on a daily wear basis. A non-inferiority margin of 10% will be used.
- 4. Subjects wearing the JJVC Investigational contact lenses on a daily wear basis will have a percentage of any grade 3 or higher slit lamp findings at all visits (scheduled and unscheduled) that is non-inferior to that of subjects wearing predicate device on a daily wear basis. A non-inferiority margin of 5% will be used.
- 5. At least 90% of eyes wearing the JJVC Investigational contact lenses on a daily wear basis will have acceptable fits across the fitting and follow-up visits.

